Secondary Objectives	To assess potential antitumor activity of single-agent M4344 when administered BIW in participants with advanced solid tumors.	Best Overall Response Objective response (OR) Disease stabilization Sum of longest diameter Evaluated by Response Evaluation Criteria in Solid Tumors (RECIST) 1.1	14.1

CCI

Part A2:

	Objective	Endpoint	IAP section
Primary	To evaluate the safety and tolerability of multiple ascending doses of single-agent M4344 administered in a twice daily (BID), once daily dose (QD), or an alternativeschedule in participants with advanced solid tumors	Safety parameters, including AEs, clinical laboratory values (serum chemistry and hematology), vital signs and ECG assessments	15.2, 15.4, 15.5, 15.6
Objectives	To determine the MTD and/or RP2D of single-agent M4344 administered in a BID or QD dose schedule in participants with advanced solid tumors	MTD and/or RP2D of single-agent M4344 administered with a twice daily or once daily dose schedule	15.1
	To evaluate PK of single-agent M4344 when administered in a BID or QD dose schedule in participants with advanced solid tumors	PK parameter estimates of single-agent M4344 administered with a twice daily or once daily dose schedule, derived from plasma concentration-time data	16
Secondary Objectives	To assess potential antitumor activity of single-agent M4344 when administered in a BID or QD dose schedule in participants with advanced solid tumors.	Best Overall Response Objective response (OR) Disease stabilization Sum of longest diameter Evaluated by Response Evaluation Criteria in Solid Tumors (RECIST) 1.1	14.1

CCI

Evaluated by Response Evaluation Criteria in Solid Tumors (RECIST) 1.1

Part B1:

	Objective	Endpoint	IAP section
Primary	To evaluate the safety and tolerability of multiple ascending doses of M4344 when administered in combination with carboplatin in participants with advanced solid tumors	Safety parameters, including AEs, clinical laboratory values (serum chemistry and hematology), vital signs and ECG assessments	15.2, 15.4, 15.5, 15.6
Objectives	To determine the MTD and/or RP2D of M4344 administered in combination with carboplatin in participants with advanced solid tumors.	MTD and/or RP2D of M4344 administered in combination with carboplatin	15.1
	To evaluate the PK profile of M4344 when administered in combination with carboplatin in participants with advanced solid tumors	PK parameter estimates of M4344 administered in combination with carboplatin derived from plasma concentration-time data	16.1
Secondary Objectives	To evaluate potential antitumor activity after administering M4344 in combination with carboplatin in participants with advanced solid tumors.	Best Overall Response Objective response (OR) Disease stabilization Sum of longest diameter Evaluated by Response Evaluation Criteria in Solid Tumors (RECIST) 1.1	14.1

6 Overview of Planned Analyses

Dose Escalation Meetings (DEMs) will determine the next dose level to be explored based on the available safety data on previous cohort(s). Prior to each DEM a data snapshot will have been taken from the clinical database as described in the Statistical Analysis Plan for DEM. Planned data displays for these meetings are described in a separate document, the Statistical Analysis Plan for DEM. There are no interim analyses currently planned for Parts A, A2, and B1 of this study, but interim analyses may be conducted for the purpose of data review and regulatory updates.

6.1 Final Analysis

All final, planned analyses identified in the Clinical Trial Protocol and in this IAP will be performed only after the last subject has completed the study with all trial data in-house, database locked for each study part (Part A2 has a separate database from Parts A and B1), and data released for statistical analyses.

A data review meeting will be held prior to each database lock. In addition, no database can be locked until this IAP has been approved.

7 Changes to the Planned Analyses in the Clinical Trial Protocol

Only analyses of Parts A, A2, and B1 of the trial are covered in this IAP. Analyses on the other parts of the trial will be described in a separate document.

8 Protocol Deviations and Analysis Sets

8.1 Definition of Protocol Deviations and Analysis Sets

Important protocol deviations are protocol deviations that might significantly affect the completeness, accuracy, and/or reliability of the study data or that might significantly affect a subject's rights, safety, or well-being.

Important protocol deviations include

- Deviations from the inclusion and exclusion criteria
- Deviations post inclusion

All important protocol deviations will be documented in the Clinical Trial Management System (CTMS) and in the Study Data Tabulation Model (SDTM) datasets, whether identified through site monitoring, medical review or data management programming.

8.2 Definition of Analysis Sets and Subgroups

Screening Analysis Set (SCR)

The screening analysis set includes all subjects who signed the informed consent form.

Safety Analysis Set (SAF)

The SAF will include all enrolled subjects who received at least 1 dose of study drug (either M4344 or carboplatin (Part B1 only)) with the actual amount > 0 mg. Analyses performed on the SAF will consider subjects' planned dose group.

Dose Limiting Toxicity (DLT) Evaluable Set

The DLT evaluable set includes all enrolled subjects who received at least one dose of M4344 and either:

- Experienced a DLT before the end of Cycle 1 (21 days after start of treatment) or
- Received the following minimum required doses of study drug(s) in Cycle 1 (21 days from start
 of treatment):
 - Part A: at least 80% (5 out of 6) of scheduled M4344 doses through the end of Cycle 1
 - Part B1: carboplatin dose on Day 1 and M4344 dose on Days 2 and 9
 - Part A2: at least 80% (34 out of 42 for BID regimen or 17 out of 21 for QD regimen) of scheduled M4344 doses through the end of Cycle 1.

Subjects who are withdrawn before they meet one of these criteria will be excluded from the determination of the MTD (and will be replaced), and thus will be excluded from the DLT evaluable set.

Full Analysis Set (FAS)

The FAS is defined as all enrolled subjects who satisfy all of the following criteria:

- received at least 1 dose of study drug with the actual amount > 0 mg
- have a baseline scan with a measurable target lesion (sum of diameters of all target lesions > 0 mm)
- have at least 1 disease assessment on treatment with a measureable target lesion (sum of diameters of all target lesions >= 0 mm); or subjects who have discontinued the study due to either progressive disease or death.

Modified Full Analysis Set (mFAS)

The mFAS is defined as all enrolled subjects who satisfy all of the following criteria:

- received at least 1 dose of study drug with the actual amount > 0 mg
- have a baseline scan with a measurable target lesion (sum of diameters of all target lesions >= 0 mm)

Pharmacokinetic Analysis Set (PAS)

The PAS will include all enrolled subjects who receive at least one dose of M4344 with the actual amount > 0 mg and provide at least one measurable post-dose concentration. Subjects will be analyzed according to the actual treatment they received. All PK analyses will be based on this analysis set.

Table 1 Summary of Analysis and Associated Analysis Set

Analyses	SCR	DLT	SAF	FAS/mFAS	PAS	CCI	CC
Disposition	V						,
Baseline Assessments			1				
Past and Concomitant Therapies			1				
Compliance and Exposure			V	3			
Efficacy				✓			

Analyses	SCR	DLT	SAF	FAS/mFAS	PAS	CCI	CC
Safety: DLTs and MTD/RP2D (primary endpoint)		V					
Other Safety and Tolerability			✓				
Pharmacokinetic Analysis	\neg				✓		

9 General Specifications for Data Analyses

Unless otherwise indicated, summary tables will be presented by study part, dose group and overall based on the analysis set of interest; listings will be presented using the same analysis sets as corresponding tables.

Pooling of centers:

Data will be pooled across centers.

Presentation of continuous and qualitative variables:

Continuous variables will be summarized using descriptive statistics, i.e. number of subjects (N), number of subjects with non-missing values, arithmetic mean (Mean), standard deviation (StdDev), median, 25th Percentile - 75th Percentile (Q1-Q3), minimum (Min), and maximum (Max).

Qualitative variables will be summarized by counts and percentages.

Unless otherwise stated the calculation of proportions will be based on the number of subjects of the analysis set of interest. Therefore, counts of missing observations will be included in the denominator and presented as a separate category.

In case the analysis refers only to certain visits, percentages will be based on the number of subjects still present in the trial at that visit, unless otherwise specified.

Definition of baseline:

The last non-missing measurement prior to the first administration of study treatment (either M4344 or carboplatin (Part B1 only)) will serve as the baseline measurement.

Definition of duration:

Duration will be calculated by the difference of start and stop date + 1 (e.g. survival time (days) = date of death – date of treatment start + 1) (if not otherwise specified).

The time since an event (e.g. time since first diagnosis) will be calculated as reference date minus date of event (e.g. time since last dose date will be calculated as the event date – the date of last dose).

Unscheduled visits:

Assessments from unscheduled visits will be used for the derivation of baseline values and worst on-treatment values. However, descriptive statistics by nominal visit or time point for safety endpoints such as laboratory measurements, ECGs and vital signs will include only data from scheduled visits per protocol.

Conversion factors:

The following conversion factors will be used to convert days into months or years: 1 month = 30.4375 days, 1 year = 365.25 days.

Handling of missing data:

Unless otherwise specified, missing data will not be replaced.

In all subject data listings, imputed values will be presented and flagged as such.

Missing statistics, e.g. when they cannot be calculated, should be presented as "nd" (not done). For example, if n=1, the measure of variability (StdDev) cannot be computed and will be presented as "nd".

Treatment day

Treatment day is defined relative to the start of a treatment. Treatment Day 1 is the day of the first administration of trial drug (M4344 or carboplatin as applicable to the study part). The day before Treatment Day 1 is defined as Treatment Day -1. (No Treatment Day 0 is defined.)

On-treatment period

The on-treatment period is defined as the date of the first dose of a trial drug (M4344 or carboplatin as applicable) until the minimum of the following: date of last dose of study treatment + 30 days and the date of death.

Definiton of Missing category

If not otherwise specified the following categories will be summarized under the missing category:

- missing
- unknown

SAS version:

All analyses will be performed using SAS® Software version 9.4 or higher.

Presentation of PK Concentration Data

PK concentration data will be descriptively summarized by part, treatment and day using: number of non-missing observations, Mean, StdDev, coefficient of variation (CV%), Min, Median and Max.

Descriptive statistics of PK concentration data will be calculated using values with the same precision as the source data, and rounded for reporting purposes only. The following conventions will be applied when reporting descriptive statistics of PK concentration data:

Min, Mean, Median and Max: 3 significant digits
 StdDev: 4 significant digits
 CV%: 1 decimal place

Presentation of PK Parameter Data

PK parameter data will be descriptively summarized by part, treatment and day using: number of non-missing observations, Mean, StdDev, CV%, Min, Median, Max, geometric mean (GeoMean), geometric coefficient of variation (GeoCV) and the 95% CI for the GeoMean (lower 95% CI for GeoMean, upper 95% CI for GeoMean).

PK parameter C_{max} will be reported with the same precision as the source data. All other PK parameters will be reported to 3 significant figures. Descriptive statistics of PK parameter data will be calculated using full precision values, and rounded for reporting purposes only.

The following conventions will be applied when reporting descriptive statistics of PK parameter data:

Min, Mean, Median, Max, GeoMean and 95% CI: 3 significant digits
 StdDev: 4 significant digits
 CV% and GeoCV%: 1 decimal place

Non-compartmental computation of pharmacokinetic parameters will be performed using the computer program Phoenix® WinNonlin® version 6.4 or higher (Certara, L.P., [name]).

10 Trial Subjects

The subsections below include specifications for reporting subject disposition and treatment/trial discontinuations. Additionally, procedures for reporting protocol deviations are provided.

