12.3 Concurrent Procedures

All concurrent procedures, which were undertaken any time during the trial, will be summarized according to the eCRF page "Non-Pharmacological Treatment or Procedures" (Parts A and B1) or "Concomitant Procedures" (Part A2).

Concurrent procedures will be derived in the same way as concomitant medications. In case the date values will not allow unequivocal allocation of a procedure as a concurrent procedure, the procedure will be considered a concurrent procedure.

All concurrent procedure data will be listed, including flags for procedures that took place prior to, on or after the date of first dose of a trial drug (M4344 or carboplatin, as applicable), or within 30 days after the last dose of a trial drug (M4344 or carboplatin, whichever was taken last).

13 Treatment Compliance and Exposure

Analysis set: SAF

Dosing information is collected from the "Study Drug Administration: VX-803 – Clinic Dose" (Parts A and B1), "Study Drug Administration Home Dose: VX-803" (Parts A and B1), "Study Drug Administration: Carboplatin" (part B1 only), "End of Dosing" (Parts A and B1), "M4344 Time of Administration" (Parts A2), and "M4344 Administration Details" (Part A2) eCRF pages.

- Part A: M4344 is taken twice a week (on treatment days 1, 4, 8, 11, 15, and 18) of a 21-day treatment cycle.
- Part A2: M4344 is taken twice a day every day of a 21-day treatment cycle. Once daily dosing and additional cohorts with a planned drug holiday may also be explored.
- Part B1:
 - Carboplatin is administered by infusion on treatment day 1 of a 21-day treatment cycle
 - M4344 is taken on treatment days 2 and 9 of a 21-day treatment cycle. An additional cohort with one additional dose on day 5 may be explored.

Total number of administrations of M4344

Total number of administrations is calculated as the sum of administrations that a subject received across cycles where actual dose received is > 0 mg or the eCRF field for "Did the subject take the dose of VX-803?" on the "Study Drug Administration Home Dose: VX-803" is marked as "Yes" or if the eCRF field for "Was VX-803 administered?" on the "Study Drug Administration: VX-803 – Clinic Dose" is marked as "Yes."

Total number of infusions of carboplatin (part B1 only)

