15.1 Maximum Tolerated Dose (Primary Endpoint)

Analysis set: DLT analysis set

The maximum tolerated dose (MTD) is defined as the highest dose for a given schedule at which there is no more than 1 DLT in 6 participants. The DLT information will be based on the "Adverse Events" eCRF page where "Dose-limiting toxicity?" = Yes.

A summary table of DLTs during the first cycle of study treatment will be provided including the following information:

- Number of subjects with no DLT
- Number of subjects with one or more DLTs

A listing of DLTs will also be provided.

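### Section 8.2 makes a participant without a DLT evaluable on dose count alone, so someone lost to observation before Day 21 is scored as a full 'no DLT'

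*SAP*

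**What the plan says.** All references are to the IAP for Parts A, A2 and B1.

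Section 8.2 gives two routes into the DLT evaluable set for a participant who has had at least one M4344 dose. The first is an event: "Experienced a DLT before the end of Cycle 1 (21 days after start of treatment) or". The second is a dose count: "Received the following minimum required doses of study drug(s) in Cycle 1", with these minimums:

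- "Part A: at least 80% (5 out of 6) of scheduled M4344 doses through the end of Cycle 1"
- "Part A2: at least 80% (34 out of 42 for BID regimen or 17 out of 21 for QD regimen"), again of scheduled doses in Cycle 1
- "Part B1: carboplatin dose on Day 1 and M4344 dose on Days 2 and 9"

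The exclusion rule follows: "Subjects who are withdrawn before they meet one of these criteria will be excluded from the determination of the MTD". Those participants are also replaced.

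Section 15.1 uses this set for a primary endpoint. The MTD is the "highest dose for a given schedule at which there is no more than 1 DLT in 6 participants". DLTs are read from a flag on the adverse event page, and the summary table has two rows: participants without a DLT, and participants with one or more.

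**The concern.** The two routes treat time differently. A DLT on Day 20 counts against the dose, but a participant nobody saw after Day 10 can count fully in its favour. The dose-count route carries no observation condition. For Parts A and A2 the reference to the end of Cycle 1 describes which scheduled doses are counted, not how long the participant is watched, and for B1 it is absent. The exclusion sentence supports this reading, because it removes only those withdrawn before a criterion is met. Anyone who leaves afterwards stays in.

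The people affected are those who leave observation after the dose threshold and before the end of Cycle 1. Since a missing DLT flag reads as no DLT, their unobserved days are treated as event-free. With a limit of one DLT in six, a single participant scored this way can decide whether a dose meets the definition.

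**Working it through.** **1. Reproduce the plan's thresholds.** 80% of scheduled doses, rounded up:

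- Part A: 0.80 × 6 = 4.8, so 5
- Part A2 BID: 0.80 × 42 = 33.6, so 34
- Part A2 QD: 0.80 × 21 = 16.8, so 17

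All three agree with Section 8.2.

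**2. Earliest day each threshold is met.** Dosing days are in Section 13. For Part A, "M4344 is taken twice a week (on treatment days 1, 4, 8, 11, 15, and 18) of a 21-day treatment cycle". Part A2 doses every day, once or twice. B1 gives carboplatin on Day 1 and M4344 on Days 2 and 9.

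| Part | Dose that meets the criterion | Earliest day | Window still to run |
|---|---|---|---|
| B1 | M4344 on Day 9 | 9 | 21 − 9 = 12 days (57%) |
| A | fifth of 6 | 15 | 21 − 15 = 6 days (29%) |
| A2 | 34th BID (34/2 = 17) or 17th QD | 17 | 21 − 17 = 4 days (19%) |

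These are the earliest possible days. A missed or delayed dose in Part A or A2 moves them later.

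**3. Look for a later safeguard.** The Section 15.1 table has no row for an incomplete window. Section 10.1 lists reasons for exclusion from analysis sets, but these participants are included and so will not appear there. Section 10.2.2 declares its own topic not applicable.

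**4. Illustrate the effect on the one-in-six rule.** The documents give no DLT rate, no DLT timing and no exit rate. The following are assumptions: true 21-day risk 1/3, six independent participants, and one B1 participant leaving on Day 10 (10 of 21 days observed, 11 not).

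Full observation: P(at most 1) = (2/3)^6 + 6 × (1/3) × (2/3)^5 = 64/729 + 192/729 = 256/729 = 0.351.

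One leaver, whose chance of a DLT while observed is q. Among the other five, P(0) = (2/3)^5 = 0.132 and P(1) = 5 × (1/3) × (2/3)^4 = 0.329. Then

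P(at most 1) = (1 − q)(0.132 + 0.329) + q × 0.132 = 0.461 − 0.329q.

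- All DLTs fall before exit: q = 1/3, P = 0.351 (no change)
- Constant hazard: q = 1 − (2/3)^(10/21) = 0.176, P = 0.403
- All DLTs fall after exit: q = 0, P = 0.461

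Two leavers. Among the other four, P(0) = 16/81 and P(1) = 32/81, so P = (1 − q)² × 48/81 + 2q(1 − q) × 16/81. This gives 0.351 (q = 1/3), 0.460 (constant hazard) and 0.593 (q = 0).

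One leaver in the other parts, constant hazard, exit right after the threshold day:

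- Part A: q = 1 − (2/3)^(15/21) = 0.251, P = 0.378
- Part A2: q = 1 − (2/3)^(17/21) = 0.280, P = 0.369

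**5. Vary the assumed risk.** One B1 leaver right after Day 9, constant hazard: at a true risk of 0.20 the probability goes from 0.655 to 0.700, and at 0.40 from 0.233 to 0.286.

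**The case against.** The strongest reply is about who is affected. A reader might infer that everyone who stops treatment early is miscounted. The document does not support that. Section 9 runs the on-treatment period to 30 days after the last dose, or to death if sooner. A last dose on Day 9, 15 or 17 therefore gives coverage to about Day 39, 45 or 47, well past Day 21. The first route in 8.2 does not require the participant to be on drug, so a DLT on Day 16 after stopping on Day 10 is counted. This stands and narrows the point to participants lost to observation. It does not remove it: an adverse event attribution window does not show that anyone was watched, and it is not a condition of evaluability.

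A reader might also infer that the B1 criterion is lax. It is not: it requires every standard Cycle 1 dose in Section 13. It is met early because of the schedule.

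Nor does the text show that escalation went wrong. Section 6 gives dose decisions to the Dose Escalation Meetings, with displays set out in a separate plan. This IAP covers the final analysis. The protocol and the meeting plan are not at hand and may require observation to Day 21, but 8.2 as written does not.

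Finally, the size is hypothetical and may be zero. That stands in full.

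**Conclusion.** The point holds for participants without a DLT who meet the dose count and then leave observation before the end of Cycle 1. As written, 8.2 and 15.1 score them as complete non-events in a primary endpoint. The direction is fixed: among these participants the error can only lower the DLT count, so if the reported MTD is affected, it is upwards. The possible unobserved stretch is longest in B1 (up to 12 of 21 days), then A (6) and A2 (4).

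The size is not known. Under the assumed risk of 1/3 with six participants, one B1 leaver on Day 10 takes the chance of passing the one-in-six rule from 35% to somewhere between 35% and 46%, according to when DLTs occur. These figures rest on assumed rate, timing and exit, and apply only if such a leaver exists. If none does, nothing changes. It should be fixed because it bears on the MTD reported at the end, but it is no evidence that any past escalation decision was wrong.

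**What to change.** In Section 8.2, add to the dose criterion for all three parts: 'and was observed for DLTs through the end of Cycle 1 (Day 21)'. Participants without a DLT who were lost to observation earlier then no longer count as 'no DLT' in the final 15.1 table. List those removed with their last day of observation. Also show the 15.1 table on the set as 8.2 now defines it, so that any difference from what the Dose Escalation Meetings worked with is visible.

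The cost is one clause, one date check, one listing and one repeated table. The real downside is that some dose groups may have fewer than six evaluable participants. The rule in 15.1 is worded for six, and Section 6.1 places this analysis after the last participant has completed, when replacement is no longer possible. State any such shortfall where the MTD is reported. If nobody left observation early, the two tables agree and the report can say so.

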10.1 Disposition of Subjects and Discontinuations

Analysis set: SCR

The disposition table will include the following information:

- Number of subjects screened (overall column only)
- Number and percentage of subjects who discontinued from the trial prior to treatment (overall column only)
- Number and percentage of subjects who took at least one dose of M4344 (SAF subjects)
- Number and percentage of subjects who took at least one dose of carboplatin (SAF subjects)
 (Part B1 only)
- Number and percentage of SAF subjects who completed M4344 overall and by completion reason (progressive disease or death)
- Number and percentage of SAF subjects who completed carboplatin overall and by completion reason (progressive disease or death) (Part B1 only)
- Number and percentage of SAF subjects who discontinued the M4344, overall and by reason for discontinuation
- Number and percentage of SAF subjects who discontinued the carboplatin, overall and by reason for discontinuation (Part B1 only)
- Number and percentage of SAF subjects that completed Long-Term Follow-Up and their status (alive, dead, or lost to follow-up) at Long-Term Follow-Up (Parts A and B1 only)
 - For subjects that are alive at Long-Term Follow-Up, their status post Safety Follow-Up will be summarized (alive without disease progression, progressed, started new anti-cancer therapy, withdrew consent).
- Number and percentage of SAF subjects who completed the trial
- Number and percentage of SAF subjects who discontinued the trial, overall and by discontinuation reason

Separate summary tables of analysis populations as well as subject enrollment for each region, country, and site will be provided.

All relevant subject disposition data will be presented in data listings including reasons for exclusion from analysis sets.

